## Study design scheme

## Schedule of study procedures

Procedure/Visit	Visit 1 (Day 1)	Visit 2* (Day 3)	Visit 3 (Day 6)	Visit 4 (Day 10)	Visit 5* (Day 21±1)	Visit 6* (Day 28±1)	Unscheduled visit**
Informed consent	+						
Registration of a study patient in the IVRS  and assignment of patient ID	+						
Complaints collection	+	+	+	+	+	+	+
Medical history	+						
Demographic data (gender and year of birth of the patient)	+						
Physical examination	+		+	+			+
Thermometry	+		+	+			+
Evaluation of 14 Symptoms Associated with COVID-19	+		+	+			+
SARS-CoV-2 rapid test	+						
Nasopharyngeal swabs for PCR	+		+	+			
Pulsoxymetry (SpO 2 )	+		+	+			+
Electronic patient diary	+	+	+	+	+	+	+
Concomitant diseases and conditions	+	+	+	+	+	+	+
Concomitant therapy	+	+	+	+	+	+	+

Procedure/Visit	Visit 1 (Day 1)	Visit 2* (Day 3)	Visit 3 (Day 6)	Visit 4 (Day 10)	Visit 5* (Day 21±1)	Visit 6* (Day 28±1)	Unscheduled visit**
Pregnancy test	+						
Inclusion/exclusion criteria	+						
Laboratory tests*** (for safety evaluation)	+		+				+****
Randomization	+						
Study drug supply	+						
Antipyretic drug and thermometer supply	+						
Study drug accountability and return			+				+****
Treatment compliance			+				+****
Safety evaluation	+	+	+	+	+	+	+
Visit completion	+	+	+	+	+	+	+
Study completion*****						+	+

 Interactive Voice Responsible System with Web Access

\* Phone survey

\*\* Unscheduled visit will be performed in case of aggravation (based on EPD), at the investigator's discretion and in case of early withdrawal (e.g. at the patient's option).

\*\*\* Include complete blood analysis and urinalysis, serum chemistry (total protein, total bilirubin, creatinine, ALT, AST, cholesterol, C-reactive protein). Performed with availability of signed PIS and ICF including the patient's consent for blood and urine sampling.

\*\*\*\* If unscheduled visit is made before visit 3.

\*\*\*\*\* In case of early withdrawal the procedure may be carried out at Visits 1-5 or at uncheduled visit.

## Statistical Analyses

SAS-[9.4]. will be used for data processing and statistical calculations.

### Samples

*Total set:* all patients who have signed ICF. This sample will consider all the recorded AEs, including those occurred prior to the study therapy.

*Safety population:* all included and randomized patients who received at least one dose of the study drug. This sample will be used for **analysis of the study treatment safety and tolerability**, as all adverse events identified after the study drug administration will be recorded.

*Full Analysis Set.* This sample includes all enrolled patients, except for those who met at least one of the following events:

- 1) non-compliance with inclusion / exclusion criteria;
- 2) patient did not take a single dose of the study drug;
- 3) lack of any data about the patient after administration of the study drug.

This sample, the most consistent with the “Intention-to-treat” principle, will be used for the **Intention-to-treat analysis (ITT analysis)** of the study therapy efficacy.

 Holder of license: OOO “NPF “MATERIA MEDICA HOLDING”, No. 70100045.

*Per protocol set.* This sample includes all patients who completed the therapy as per the study protocol and completed all the scheduled visits. This set will be used for the ***Per Protocol analysis (PP analysis)*** of the study therapy efficacy. *PP set* will not include the patients with their data completely or partially invalid for analysis due to a protocol deviation.

The list of deviations that may result in complete or partial invalidity of data is developed by a medical expert jointly with a biostatistician according to the study design.

The deviations that may result in partial or complete invalidation of the study subject's data.

1. Inappropriate distribution/supply of the study drug.
2. Prescription of prohibited therapy.
3. Increase or decrease in the study drug dosing by  $\geq 25\%$ .
4. Inability to assess the patient's compliance using the formula (e.g. loss of pack with the product).
5. Major discrepancies between source documents and CRF identified during monitoring or another authorized inspection.
6. Violation of the procedure of obtaining informed consent.
7. Non-compliance with the clinical study protocol procedures.
8. Inability to collect all the patient's data used for evaluation of the study endpoints (e.g. lack of records in source documents required for verification of inclusion/exclusion criteria, safety and efficacy criteria).
9. Any other protocol deviations covered by the term “major deviation”.

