If more severe symptoms are presented, the patient is not included in the study. The therapeutic approach is determined by the current edition of the clinical recommendations of the Ministry of Health of the Russian Federation «Prevention, diagnosis and treatment of a new coronavirus infection (COVID-19)».

At visit 1 (Day 1), in addition to rapid COVID-19 test and SpO2 measurement, the investigator collects complaints and medical history of the patient, performs objective examination including vital signs (blood pressure, heart rate and breathing rate), records concomitant diseases and concomitant therapy, performs nasopharyngeal swabs for PCR (for detection SARS-CoV-2), laboratory tests (if the patient gave his/her consent for blood and urine sampling).

Patients who meet all the inclusion criteria and do not have exclusion criteria at Visit 1 (Day 1) are randomized into one of two groups: patients in group 1 receive Raphamin for 5 days; patients in group 2 receive placebo according to the Raphamin regimen.

If positive PCR test is received (confirmation of new coronavirus disease COVID-19), the patient continues to participate in the study. If PCR result is negative, the patient completes participation in the study ahead of schedule, and his further therapy is determined by the investigator in accordance with the standards of care.

Electronic patient diary (EPD) is utilized in the study, in which morning and evening axillary temperature records are made with the time of measurement. The sponsor provides a classical mercury-free thermometer to each patient. In addition, presence and severity of the disease symptoms according to the scoring system «Assessment of 14 Common COVID-19-Related Symptoms», antipyretics administration and probable worsening of disease duration should also be recorded in EPD. All patients are provided with paracetamol. The physician instructs the patient

how to fill in the diary. The EPD is available for filling in within 28 days of participation in the study.

Overall, patients are observed for 28 days (screening and randomization up to 1 day, treatment for 5 days, follow-up till 28th day).

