## **Inclusion and exclusion criteria**

### ***Inclusion criteria***

1. Male and female patients aged 18-75 years old.
2. Diagnosis of new coronavirus infection COVID-19 based on medical examination: axillary temperature  $>37.5^{\circ}\text{C}$ , symptoms of upper respiratory infection,  $\text{SpO}_2 \geq 95\%$ , no symptoms of moderate or severe levels.
3. The minimal baseline score for COVID-19-related symptoms defined as follows: at least two symptoms with a score of 2 or higher, with the exception of taste and smell where subjects may have a score of 1 or higher, and the absence of shortness of breath (difficulty breathing).
4. Positive rapid test for SARS-CoV-2 (COVID-19).
5. The first 24 hours from the disease onset.
6. Patients giving their consent to use reliable contraception during the study.
7. Signed patient information sheet (informed consent form).

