### ***Evaluation of sample size***

It is expected that out of 798 patients randomized 712 patients will complete the study per protocol. Taking into consideration the expected screening failures, the informed consent should be obtained from 838 patients.

The sample size was assessed on the basis of the following rules and assumptions:

1. Statistical provisions.
  - 1.1 the power of the statistical tests “ $P = (1 - \beta)$ ” is assumed to be 80% (the probability of correct rejection of the null hypothesis is 0.8);
  - 1.2 the probability of a type I error “ $\alpha$ ” is allowed to be less than 5% (the probability of false acceptance of an alternative hypothesis is less than 0.05);
  - 1.3 the study **does not plan** unblinded interim analysis;

---

 If, considering the lack of some data in primary endpoint variable, the fact of reaching the primary endpoint by the patient can still be determined, the patient will be eligible for PP analysis (e.g. the diary lacks some records but the time of recovery can still be determined).

 No more than 5% patients who signed PIS and ICF are expected to be screening failures for various reasons.

- 1.4 the applied statistical tests for group comparisons are two-sided, unless stated otherwise;
- 1.5 the sample size is calculated based on the assumptions on the expected effect declared in the primary endpoint of this protocol;
- 1.6 the ratio between the sample sizes of the study drug and placebo groups is 1:1 (1 study drug patient - 1 placebo patient);
- 1.7 statistical hypotheses: null and alternative hypotheses about the superiority of the study drug over placebo using the applied dosing regimen:

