**primary endpoint:**

$$H_0: OR_{12} = 1$$

$$H_a: OR_{12} \neq 1$$

where : OR12 – is odds ratio for an event occurrence in Raphamin and Placebo groups (the lower, the better).

The following SAS program code was used to determine the required sample size:

*SAS code performed:*

```
proc power;  
twosamplefreq test=lrchi  
OR=0.5  
refp=0.15  
power=.8  
alpha=.04  
npergroup=.;  
run;
```

- 1.8 Full sample size is determined using the formula:

$$N = N_{pp} / (1 - R_w),$$

where N – the final sample size;

**Npp** – result of calculation in cl. 1.7, i.e. scheduled number of the patients completing the study per protocol;

**Rw** – withdrawal rate.

2. Assumptions on expected effects of the clinical study: Odds ratio for the event occurrence in Raphamin and Placebo groups is expected to be no more than **0.5** at population event frequency of at least **0.15** [32-34].

---

 The analysis stipulates for obligatory assessment and accounting for effects of additional factors: history of vaccination and age/age groups of the subjects.

 In assumption of reduced proportion of severe form in case of strain change (to Omicron) and based on the following sources:

Therefore, the number needed to compare study drug and placebo will be **712** patients for both groups. Given potential withdrawal of at least 15% patients (**Rw = 0.15**) during the study for various reasons, at least **838** subjects will be required to sign informed consent allowing to randomize **798** patients with **399** subjects per group (see cl. 1.8).

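### The Full Analysis Set keeps dosed patients whose Visit 1 PCR is negative, although the protocol treats COVID-19 as unconfirmed in them and stops their follow-up

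*Combined protocol and SAP*

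**What the plan says.** - **Entry.** Inclusion criterion 4 asks for "Positive rapid test for SARS-CoV-2 (COVID-19"). No inclusion criterion mentions PCR. Criterion 2 rests the COVID-19 diagnosis on the medical examination.
- **PCR.** Under Study design and in the Schedule of study procedures, the first swab is taken at Visit 1 (Day 1), the randomisation visit. A positive result is described as confirming COVID-19. Otherwise, "If PCR result is negative, the patient completes participation in the study ahead of schedule".
- **Withdrawal.** Criteria for Withdrawal or Termination lists a negative PCR as item 2, apart from screening failure (item 1) and eligibility error (item 10).
- **Analysis set.** Under Samples, the FAS rule reads "This sample includes all enrolled patients, except for those who met at least one of the following events". The events are a breach of the entry criteria, no dose taken, and no data at all after dosing. This set carries the ITT efficacy analysis. The per-protocol set requires completion of all scheduled visits.
- **Endpoints.** The primary endpoint is progression by Day 28. An additional endpoint is the proportion with a negative PCR on Days 6 and 10. The Statistical Analyses section does not say how a missing Day 28 outcome is scored.

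**The concern.** The objective is treatment of COVID-19, and the plan uses PCR to decide who has it. Yet the set for the main efficacy analysis keeps patients whom the protocol has sent home as unconfirmed. Three things follow.

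- Most of these patients have no Day 28 outcome, so their contribution to the primary odds ratio depends on a scoring choice that is not written down.
- Some may count as progressions of a different illness. The moderate-severity criteria in the endpoint footnote are not specific to COVID-19. They include a temperature above 38.0 °C, while entry already requires more than 37.5 °C.
- Patients negative at baseline sit in the denominator of the Day 6/10 negative-PCR endpoint. Any of them counted as negative is a success that treatment could not have produced.

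Events that occur equally in both arms among these patients pull the odds ratio towards 1.

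**Working it through.** **Inputs from Evaluation of sample size and its SAS code**

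- Placebo rate 0.15 and odds ratio (OR) 0.5. The Raphamin odds are 0.5 × 0.15/0.85 = 0.0882, so the rate is 0.0882/1.0882 = 0.0811.
- Test: "twosamplefreq test=lrchi" (likelihood-ratio chi-square). Sidedness: "the applied statistical tests for group comparisons are two-sided, unless stated otherwise".
- Alpha 0.04 in the code; the text says the type I error "is allowed to be less than 5" per cent. Power 0.80.
- Allocation: "the ratio between the sample sizes of the study drug and placebo groups is 1:1".
- Attrition: "Given potential withdrawal of at least 15" per cent, counted from consent to per-protocol completion.

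**Assumptions (not in the documents)**

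- f, the PCR-negative share of dosed patients: 2%, 5% or 10%.
- b, the event rate scored for these patients, the same in both arms: 0 (all non-events) or 0.15 (the plan's placebo rate).

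**Formula.** With K(p, q) = p ln(p/q) + (1 − p) ln[(1 − p)/(1 − q)] and p̄ the mean of the two rates, λ = 2n[K(p_placebo, p̄) + K(p_Raphamin, p̄)]. Power is the probability that a noncentral chi-square with 1 df and noncentrality λ exceeds 4.218, the critical value at alpha 0.04.

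**Step 1: the plan's own figure.** At n = 356 per arm, λ = 8.386 and power is 80.0%; at 355 it is 79.9%. So 356 per arm and 712 in total reproduce exactly, and 712/0.85 = 837.6, which rounds up to 838. There is no arithmetic error in the plan here.

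**Step 2: where PCR-negative patients fall.** The 712 are per-protocol completers, so a patient stopped early cannot be among them. The plan randomises 798 and allows 798 − 712 = 86 losses (86/798 = 10.8%) for all causes, without itemising PCR negatives. At f = 5% they would be 0.05 × 798 ≈ 40 of the 86; at f = 10%, about 80.

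**Step 3: keep or exclude, starting from 399 randomised per arm with no other loss.** With f = 0, λ = 9.399 and power is 84.4%. If these patients are excluded, n becomes 399(1 − f) and the rates stay at 0.15 and 0.0811. If they are kept, n stays at 399 and each rate becomes (1 − f)p + fb.

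| f | Handling | n per arm | Placebo rate | Raphamin rate | OR | Power |
|---|---|---|---|---|---|---|
| 2% | excluded | 391.0 | 0.150 | 0.0811 | 0.50 | 83.68% |
| 2% | kept, b = 0 | 399 | 0.1470 | 0.0795 | 0.50 | 83.58% |
| 2% | kept, b = 0.15 | 399 | 0.150 | 0.0825 | 0.51 | 82.69% |
| 5% | excluded | 379.05 | 0.150 | 0.0811 | 0.50 | 82.50% |
| 5% | kept, b = 0 | 399 | 0.1425 | 0.0770 | 0.50 | 82.25% |
| 5% | kept, b = 0.15 | 399 | 0.150 | 0.0845 | 0.52 | 79.89% |
| 10% | excluded | 359.1 | 0.150 | 0.0811 | 0.50 | 80.36% |
| 10% | kept, b = 0 | 399 | 0.1350 | 0.0730 | 0.50 | 79.85% |
| 10% | kept, b = 0.15 | 399 | 0.150 | 0.0880 | 0.55 | 74.73% |

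For example, the last OR is (0.0880/0.9120)/(0.15/0.85) = 0.0965/0.1765 = 0.55.

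**Step 4: gain from excluding, before rounding to one decimal.** At 2%, 0.10 to 0.99 points. At 5%, 82.50 − 82.25 = 0.25 to 82.50 − 79.89 = 2.61 points. At 10%, 80.36 − 79.85 = 0.51 to 80.36 − 74.73 = 5.63 points.

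**The case against.** **ITT keeps randomised patients.** It does, and retaining rapid-test-positive, dosed patients is defensible in principle. Dilution of this kind also does not favour the drug. But ITT normally keeps the patient and follows the outcome. This plan stops follow-up and then retains the patient for a Day 28 endpoint.

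**The per-protocol set already drops them.** True, and the trial is sized on that set. But it also drops other non-completers and protocol deviators, so no set isolates confirmed infection under near-ITT rules.

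**They could be removed as failing inclusion criterion 2.** That criterion bases the diagnosis on the medical examination, and the withdrawal list separates a negative PCR from an eligibility error. At most the text is ambiguous. Patients never dosed, or with no post-dose record, do leave the FAS. However, the diary runs from Day 1 and there is a Day 3 call, so most dosed patients probably have some record.

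**Time to recovery can be censored.** The survival methods listed under Non-parametric criteria allow this, so that endpoint is less exposed.

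**Missing Day 28 outcomes are a wider gap.** This also stands. The gap affects every early withdrawal, and excluding one subgroup does not close it.

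Two stronger readings are tempting. A reader might compare the plan's 80% at 356 per arm with a figure diluted at the same 356 and blame the whole fall on the FAS rule. The 356 are completers, and most of the fall comes from having fewer confirmed patients, which exclusion cannot restore. A reader might also score every PCR-negative patient as a progression, which at 356 per arm would put power at 63% (f = 5%) or 50% (f = 10%). The documents contain no rule that a missing outcome counts as failure, so those figures have no support.

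**Conclusion.** The point holds as a gap in the FAS definition. As written, dosed PCR-negative patients with any post-dose data enter the ITT efficacy analysis without confirmed COVID-19, and usually without the primary outcome.

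The cost in power is modest: about 0.3 to 2.6 points if 5% are negative and about 0.5 to 5.6 points if 10% are, compared with excluding them. The lower end, with all scored as non-events, is almost nothing and leaves the OR at 0.50. The upper end moves it to 0.52 or 0.55. Stronger than the power argument is that the ITT odds ratio would depend on an unwritten scoring choice for patients outside the target disease, and that the Day 6/10 PCR endpoint would include patients already negative at baseline.

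This rests on assumed values of f and b, on 399 per arm with no other loss, and on the swab preceding the first tablet. That last point is inferred from the order of the Visit 1 procedures; the documents do not state it.

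**What to change.** Add a fourth FAS exclusion under Samples: a negative PCR on the Visit 1 swab, decided from the laboratory result while the trial is still blinded. State in Study design that this swab is taken before the first dose, so that the exclusion cannot depend on treatment. Use the resulting PCR-confirmed set for the primary, secondary and Day 6/10 PCR analyses. Keep the excluded patients in the safety population, report their number by arm, and run the all-dosed set as a sensitivity analysis with the scoring of their missing Day 28 outcomes written down.

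The cost is one line in the FAS definition, one clarifying sentence and one sensitivity table. The PCR result is already scheduled for every patient. The downside is a slightly smaller primary analysis set and a departure from strict ITT, which the sensitivity analysis covers.

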During the study, six visits are planned: on days 1, 3, 6, 10, 21, and 28 (visits 1, 2, 3, 4, 5, and 6). Visits 1, 3, and 4 are in person (visits to the patient or visits to the medical center) when the physician examines the patient and monitors EPD records. At visit 3, the patient's adherence to treatment is assessed and laboratory tests are performed. Visits 2, 5 and 6 are phone surveys to determine the patient's condition, presence/absence of complaints. In case of worsening of disease duration, the physician makes an extra visit. Patients with COVID-19 progression to more severe level as well as hospitalized patients are considered as reaching the study endpoints and terminate participation in the study ahead of schedule. The therapeutic approach is determined by the current edition of the clinical recommendations of the Ministry of Health of the Russian Federation «Prevention, diagnosis and treatment of a new coronavirus infection (COVID-19)».

During the study, the use of paracetamol and medicines for the treatment of concomitant diseases is allowed, with the exception of the drugs specified in the section «Prohibited concomitant treatment».

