### **Criteria for Withdrawal or Termination**

1. Screening failure.
2. Negative PCR test for SARS-CoV-2.
3. Failure or refusal of the patient to follow the protocol.
4. Deviation from personal visit schedule by more than 1 day.
5. The necessity to use medications not permitted in the study.
6. An adverse event requiring discontinuation of the study drug.
7. Patient's decision to withdraw early for lack of efficacy or other reasons.
8. Pregnancy.

9. Cases not stipulated in the protocol where the investigator decides that further participation may harm the patient.
10. Eligibility error.
11. Participation in any other clinical study.
12. Unblinding.

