### **Number of patients**

It is planned to include 838 patients, 798 of them will be randomized which is expected to yield at least 712 patients (356 per Raphamin and Placebo groups) completing all the protocol procedures.

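### Read literally, the per-protocol set excludes patients whose primary event is found before Visit 6, and no sentence in the plan reconciles this

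*Combined protocol and SAP*

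**What the plan says.** The Samples section defines the PP set, which is used for an efficacy analysis: "This sample includes all patients who completed the therapy as per the study protocol and completed all the scheduled visits". The primary endpoint is progression by Day 28. Six visits are planned, the last on Day 28. Under Study design, patients who progress or are hospitalised "are considered as reaching the study endpoints and terminate participation in the study ahead of schedule".

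Three other places bear on how such patients are treated:

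- Footnote 4 belongs to item 8 of the deviation list under Samples, which concerns endpoint data that could not be collected. It says that if, despite some missing data, "the fact of reaching the primary endpoint by the patient can still be determined, the patient will be eligible for PP analysis".
- The section "Criteria for Withdrawal or Termination" lists neither progression nor hospitalisation.
- The notes to the Schedule of study procedures say "Unscheduled visit will be performed in case of aggravation (based on EPD"), and name early withdrawal as a separate reason for that visit. The study-completion row is marked at the unscheduled visit.

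The sample size appears under Number of patients as 798 randomised, "which is expected to yield at least 712 patients (356 per Raphamin and Placebo groups) completing all the protocol procedures". Evaluation of sample size says "712 patients will complete the study per protocol" and defines N_pp, the output of the power calculation, in the same terms.

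**The concern.** A patient who progresses before Visit 6 follows the protocol by leaving, and by leaving fails the visit condition for PP. If the event falls within the 5-day course, the same patient also fails the therapy condition. The literal PP set is therefore made up of patients without the event, plus the few whose event is first found at Visit 6. That is selection on the primary outcome.

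Two analysts could build opposite PP sets from this text, one with the primary events and one with almost none. The documents do not say whether FAS or PP is primary for efficacy. If the reading were settled only after the data were seen, there would be avoidable discretion over which events count. The description of the 712 under Number of patients invites the same literal reading.

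**Working it through.** **Inputs.** From Evaluation of sample size: odds ratio 0.5, reference event rate 0.15, likelihood-ratio chi-square test, two-sided alpha 0.04, power 0.80, 1:1 allocation, R_w = 0.15 (of which 5% is screening failure, footnote 8), 798 randomised (399 per group).

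**1. Reproduce the plan's figure.** Raphamin event rate: odds = 0.5 × 0.15/0.85 = 0.0882, so p_R = 0.0882/1.0882 = 0.0811. With p̄ = (0.15 + 0.0811)/2 = 0.1155, the noncentrality is λ = 2n Σ [p ln(p/p̄) + (1 − p) ln((1 − p)/(1 − p̄))], summed over the two arms. At n = 356, λ = 8.386 against a critical value of 4.218, and power is 0.800 (0.799 at n = 355). So 356 per group, 712 in total. 712/0.85 = 837.6, rounded up to 838. The stated numbers reproduce.

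**2. Events inside the 712.** 356 × 0.15 = 53.4 and 356 × 0.0811 = 28.9, together about 82. Event-free: 712 − 82.3 = about 630.

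**3. Events among the 798.** 399 × (0.15 + 0.0811) = 92.2. If all are found before Visit 6, at most 798 − 92.2 = about 706 can make every visit, which is below 712 even with no other loss.

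**4. The loss allowance.** 798 − 712 = 86, or 10.8% of those randomised. If a share f of events is first found at Visit 6, event exits are 92.2 × (1 − f). These fit within 86 only if f is at least 1 − 86/92.2 = 6.7%, and only if nobody is lost for any other reason. The plan does expect other losses; for example, PCR-negative patients leave after randomisation. If event patients count as completers, 712 of 798 is consistent.

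**5. What strict PP would estimate.** It keeps n(1 − p) event-free patients and n·p·f event patients per arm, so the event odds are f·p/(1 − p). The PP odds ratio is then 0.5 × f_R/f_P. With equal f it stays at 0.5 and only precision is lost. With unequal f, it mixes the effect with event timing: f_R = 20% and f_P = 10% would give 1.0. With f = 0 in both arms there are no events and no estimate.

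**6. Illustration of lost precision.** The documents give no event timing, so f is an assumption. The basis is the plan's 356 per arm, with the same f in both arms and an unadjusted Fisher exact test at alpha 0.04 by full enumeration:

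| f | Events kept (of 82) | Power |
|---|---|---|
| 5% | about 4 | 4% |
| 10% | about 8 | 11% |
| 20% | about 16 | 20% |
| all events kept | about 82 | 77% |

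**7. Does any text waive the condition?**

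- Footnote 4 answers a different question. A progressor's primary endpoint is known; the obstacle is the membership sentence, which the footnote does not mention. Its example, time of recovery, relates to a secondary endpoint.
- The withdrawal list and the schedule notes imply that exit at the event is not a withdrawal. They do not say that it counts as completing therapy or visits.
- The regimen is 8 + 4 × 3 = 20 tablets. A patient who exits after Day 3 has taken 8 + 3 + 3 = 14, which is 30% fewer. Deviation 3 (dosing changed by 25% or more) could then be read as a further ground for exclusion.

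**The case against.** The strongest reply is that the literal reading is strained. The protocol itself directs the exit, so such a patient missed no visit that still applied. Footnote 4 sits inside the PP rules and keeps patients with incomplete data if endpoint status is known; a documented event is a stronger case. Progression is not a withdrawal criterion, and study completion can be recorded at the visit held for aggravation. A PP set with almost no events would also be noticed at once.

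Most of this stands as evidence of intent, and the sponsor probably means to keep these patients. It does not amount to a rule, because no sentence lifts either condition.

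The objection also limits the point in three ways:

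- Under Evaluation of sample size, completing per protocol can be read to include exit at the event. Only the phrase under Number of patients clearly conflicts with Study design.
- The power figures are not those of the planned primary analysis. Footnote 6 requires vaccination history and age to be accounted for, and nothing in the documents supports any particular f.
- Counting every hospitalisation exit as completion would not be enough. Hospitalisation is a separate secondary endpoint, so a patient hospitalised without recorded progression could be a completer with undetermined primary status.

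**Conclusion.** The conflict is real and confined to the PP definition and the wording around the 712. As written, PP excludes patients because they had the primary event before Visit 6, and such a set could neither support nor question the ITT result. At the plan's assumed rates this concerns about 82 of 712 analysed patients, or about 92 of 798 randomised, less those first found at Visit 6. It should be corrected, but it is a defect of definition, not evidence that events will be dropped.

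A reader might infer more than the documents support:

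- That the sample size is wrong or the trial underpowered. It is not: the 712 reproduces, and the calculation needs the event patients inside it.
- That the main efficacy result is compromised. The FAS has no visit-completion condition and keeps these patients.
- That PP power falls to a particular value. That depends on event timing, which the documents do not give, so the table is illustrative only.

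**What to change.** 1. Under Samples, define PP as patients with no major deviation up to the primary event or Day 28, whichever comes first. State that exit for progression under Study design counts as completing therapy and visits.
2. State how a patient who exits for hospitalisation without recorded progression is classified for the primary endpoint, and apply the same classification in FAS and PP.
3. Under Number of patients, describe the 712 as patients evaluable for the primary endpoint.
4. Under Evaluation of sample size, including the definition of N_pp, make clear that completing per protocol includes exit at the primary event.

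This changes protocol and SAP wording only. It needs no additional patients or data and leaves the exit rule and the sample size as they are. It should be settled before unblinding, so that the PP set does not depend on a reading chosen with the results in view.
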